**BASELINE FORM 4/8****Concurrent diseases at this visit**

History of cancer .....		0-no; 1-yes; default=no
Active cancer .....		if yes: with metastases:  0-no; 1-yes
under chemotherapy:  0-no; 1-yes		
Diabetes .....		
Hypertension .....		
TIA/stroke/peripheral embolism .....		
Ischemic heart disease .....		
Left ventricular hypertrophy .....		
Heart failure .....		
Peripheral vascular disease .....		
History of angioplasty/surgery .....		
Chronic inflammatory diseases .....		
Chronic respiratory diseases .....		
Cirrhosis + esophageal varices .....		
Kidney failure .....		
Hypothyroidism .....		
Hyperthyroidism .....		
Other diseases .....		

**Current medications (used for at least 3 months) at this visit**

ASA <250 mg/day .....		0-no; 1-yes [default=no]
Other antiplatelets .....		
Antiarrhythmic agents .....		
Antidiabetics .....		
Antidyslipidemic agents .....		
ACE inhibitors .....		
Sartans .....		
Beta-blockers .....		
Diuretics .....		
Calcium antagonists .....		
Other antihypertensive agents .....		
Nitrates .....		
Digitalis .....		
Proton pump inhibitors .....		
Antiviral agents .....		
Immunosuppressives .....		
Steroids .....		
Drugs for thyroid disorders .....		
Analgesic agents .....		
Anti-inflammatory drugs .....		

## Vascular risk factors at this visit

Smoking.....	 0-no; 1-yes; 9-N/A	if yes: less than 10 cigarettes per day 
		10-20 cigarettes per day 
		more than 20 cigarettes per day 
Thrombophilia test.....	 0-negative; 1-positive; 9-not done	
if positive: specify which.....		Factor V Leiden 
		Factor II G20210A 
		Protein C deficiency 
		Protein S deficiency 
		AT deficiency 
		LAC+aCL Anti-Beta2GP1 
		Hyperhomocysteinemia 
		JAK2 
		other 
		(specify other) .....
		[0-negative; 1-positive; 9-not done; default: N/A]
Dementia (assumed absent unless there is evidence it is present)...	 0-no; 1-yes	
Chronic bed rest.....		
Wheelchair.....		
Tendency to falls.....		
History of major bleeding .....	 if yes:	cerebral hemorrhage 
		gastrointestinal bleeding 
		retroperitoneal hemorrhage 
		ocular haemorrhage 
		intra-articular haemorrhage 
		hemoglobin drop by 2 or more g/dL 
		transfusion 
Living alone .....		
Absence of family or social support.....		
Family history of thromboembolism .....		
Family history of coronary disease .....		
Family history of TIA/stroke.....		
Alcohol consumption .....	 if yes: 1 unit per day	
	2 units per day	
	more than 2 units per day	
1 unit = 1 glass (125 ml) of wine or 1 can (330 ml) of beer or 1 tumbler (30 ml) of spirit		

## BASELINE FORM 6/8

## Other clinical information

Body weight (kg): |\_|\_|\_|\_|.|\_|  
check limits: 40-200

height (cm): |\_|\_|\_|\_|  
check limits: 90-230

BMI: |\_|\_|.|\_|  
computed: kg/m^2

If available: last creatinine value recorded during the 3 months before the visit:

Creatinine: units  mg/dL (default)  µmol/L  
value: |\_|\_|.|\_|\_|\_|  
clearance: |\_|\_|\_|.|\_|  
computed; Cockroft-Gault formula

if creatinine is in µmol/L multiply by 0.01131222; round to 3 digits

clearance (in mL/min): 
$$\frac{(140 - \text{age [in years]}) \times \text{body weight [in kg]}}{72 \times \text{creatinine [in } \frac{\text{mg}}{\text{dL}}\text{]}} \times 0.85 \text{ if female (no change if male; missing if sex is NA)}$$

**Maintenance anticoagulation treatment prescribed after the index event  
(the treatment to continue-resume/stop/change at this visit)**

**WINDOWS FOR CLASS VKA, LMWH, NOACS – FOR DATABASE USE ONLY**

The following tables are called-in upon selection of the drug class.

The operator can select one only from each of these, and is requested to input the daily dose as number CHECK supplies the acceptable range for the number. Doses out of range require a warning-

TO BE RECORDED: ATC CODE and DAILY DOSE. There should be not more than one per class (VKA, LMWH, NOAC); two of them may be empty if OTHER is empty; all three can be empty if OTHER is marked.

**VKA**

Name	unit	DAILY DOSE	ATC code	CHECK
dicoumarol	mg		B01AA01	25-400
phenindione	mg		B01AA02	25-400
warfarin	mg		B01AA03	1.25-30
phenprocoumon	mg		B01AA04	0.5-12
acenocoumarol	mg		B01AA07	1.25-20
ethyl biscoumacetate	mg		B01AA08	125-2400

**LMWH**

Name	unit	DAILY DOSE	ATC code	CHECK
bemiparin	Ux1,000		B01AB12	5-10
certoparin	Ux1,000		B01ABXX	8-16
dalteparin	Ux1,000		B01AB04	0.15-18
enoxaparin	Ux1,000		B01AB05	6-15
nadroparin	Ux1,000		B01AB06	3-8.5
parnaparin	Ux1,000		B01AB07	4-12.8
reviparin	Ux1,000		B01AB08	5-10.5
tinzaparin	U/kg		B01AB10	>=175

**NOACS**

Name	unit	DAILY DOSE	ATC code	CHECK
rivaroxaban	mg		B01AF01	5-30
apixaban	mg		B01AF02	5-20
edoxaban	mg		B01AF03	30-60
dabigatran	mg		B01AE07	220-300

## Decision on next therapy

### **From this visit onward, the therapy will be:**

### **Please specify:**

Treatment prescribed in this visit:	Box “replaced_1”
vitamin-K antagonist	 0-no; 1-yes; if yes open window VKA
low molecular weight heparin	 0-no; 1-yes; if yes open window LMWH
direct anticoagulants (NOACS)	 0-no; 1-yes; if yes open window NOACS
other	 0-no; 1-yes; if yes open window “other”

Treatment prescribed in this visit:	Box "replaced_2"	
aspirin	 0-no; 1-yes	
if aspirin=yes:	daily dose:	 75-175 mg
ATC: B01AC06	 176-250 mg	
	 251-500 mg	
	 >500 mg	
sulodexide	 0-no; 1-yes	
if sulodexide = yes:	daily dose:	 500 LSU
ATC: B01AB11	 1000 LSU	
other	 0-no; 1-yes; if yes open window "other"	

**Please specify whether compression therapy is prescribed:**

no:  0   yes:  1   specify mmHg recommended: |        | [text]

**Reasons for taking this decision  
(please tick all what applicable)**

No need of further treatment		0-no; 1-yes; default=no
Risk of thromboembolic recurrence		specify:  high-medium  low [HELP BOX FOR CRITERIA]
Risk of bleeding		specify:  high  medium  low [HELP BOX FOR CRITERIA]
Major bleeding event during treatment		
Difficulty to maintain the proper INR		
Consideration of patient's age		
Presence of Post Thrombotic Syndrome		
Presence of thrombophilia		specify: _____ [text]
Familiarity for venous thromboembolism		
Implantation of vena cava filter		
Presence of pulmonary hypertension		
Worsening of general conditions (not cancer)		
Worsening/onset of renal insufficiency		
Tendency to falls		
Presence of cancer		
Onset of contraindications		specify: _____ [text]
Decision by the patient's family doctor		
Choice of the patient		
Cost for the patient		
Positive D-dimer value		specify value:  _ _  D-DU  FEU 
Negative D-dimer value		specify value:  _ _  D-DU  FEU 
[if D-dimer value specified, one of the units MUST be specified]		
Patient involved in choosing the prescribed therapy		0-no; 1-yes; default=no
Patient's GP involved in choosing the prescribed therapy		0-no; 1-yes; default=no
Planned duration of this therapy:  not applicable [if decision=2, only possible choice]  not defined  to be evaluated  defined; specify:  _ _ _    months  years		

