### 8.2.2 Inclusion criteria

Subjects meeting all of the following criteria qualify for entry into the study:

- a) subjects who provided a written informed consent and authorization for disclosure of protected health information;
- b) male and female adult or elderly subjects ( $\geq 18$  years at the time of signing the informed consent; no upper limit);
- c) of any ethnicity;
- d) with a first-ever event of provoked or unprovoked DVT of the lower limbs and/or PE treated with anticoagulants (NOACs, VKAs, or LMWHs) according to the local procedures (usually for 3 to 12 months) and to be re-evaluated to decide the treatment to be prescribed after this period;
- e) for whom the center possesses all the data relevant to the index event;
- f) having a permanent reference contact.

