###### **d. treatment information**

This includes type, dosage and duration of the maintenance anticoagulation performed; type, dosage and planned duration of the new treatment proposed, if any, and the classification of the reasons considered by the investigator for the decision taken.

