## 10.3 Populations

As usual in the observational studies, the analyses will be performed on the total sample monitored. Only subjects specifically indicated by the Steering Committee as major, irreconcilable deviation will be excluded from analysis (§ 11.1). Missing data will not be replaced. Subgroup analyses are not anticipated, however – given the exploratory nature of the study – unplanned subgroups analyses may be performed *post-hoc*, upon indications by the Steering Committee.

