### 10.4.3 Secondary endpoints

The secondary endpoint analyzable at the completion of recruitment is the reason(s) justifying the choice analyzed in 10.4.2. These will be tabulated by choice and compared, if appropriate, by chi square test or by ordinal logistic regression. Unplanned *post-hoc* subgroup analyses may be performed if requested by the Steering Committee.

The other secondary endpoints include the frequency of thromboembolic complications and the frequency of bleeding complications or death for any reason. These will be analyzed at the completion of each year of observation (full year of observation of the last subject entered into the long-term follow-up). The interim results will be used by the DMSB to decide on whether the observation has to continue or must be stopped. The final analysis will be adjusted for multiplicity using the nominal critical P value of 0.048.

Event rates will be reported at the available observations as proportion, stratified by sub-population, with the relevant confidence interval. Deviations from the expected rate of events will be analyzed by chi square and/or time to event by survival analysis. If appropriate, subgroups will be analyzed with the Cox survival model. Impact of putative predictors as indicated by the Steering Committee will be analyzed by logistic regression and/or Cox proportional-risk model.

Since clinically-relevant non-major bleeding may not be a reason for interrupting the follow-up, and minor bleedings are not a reason for interruption, it is possible that the number of bleeding events per subject can be submitted to analysis by Poisson regression.

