#### IN CASE OF DEEP VEIN THROMBOSIS:

location of the index episode:

(select all what applicable)

[only if type=1, 2 or 3;

at least one must be checked;

if both right and left are checked, request

confirmation]

[0=no; 1=yes]

VEIN	.....	left	.....	right
external iliac	.....		.....	
common femoral	.....		.....	
superficial femoral	.....		.....	
deep femoral	.....		.....	
popliteal	.....		.....	
posterior tibial	.....		.....	
peroneal	.....		.....	
anterior tibial	.....		.....	
medial gastrocnemius	.....		.....	
lateral gastrocnemius	.....		.....	
soleal	.....		.....	
saphenous (great and/or small)	.....		.....	

**BASELINE FORM 2/8****Index episode of venous thromboembolism  
additional information**

Superficial vein thrombosis:	 0-no 1-yes
In case of pulmonary embolism: Recent ( $\leq$ 1 month) echocardiography:	 If yes: date  _ / _ / _ _ _  0=no/1-yes – is NA with date blank if Type of event = 1 or 2
Signs of pulmonary hypertension:	 0=no/1-yes – is NA with date blank if Type of event = 1 or 2
HELP BOX: "PULMONARY HYPERTENSION"	

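### The comparison of the INR reason between choices can reflect who was on a VKA, because subjects without a VKA are counted as not citing it

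*Combined protocol and SAP*

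**What the plan says.** - **Eligible treatments.** Section 8.2.2 admits subjects "treated with anticoagulants (NOACs, VKAs, or LMWHs) according to the local procedures", so the sample mixes three maintenance classes.
- **The reason item.** Appendix IV (CRF template, reasons for the decision) lists "Difficulty to maintain the proper INR" among boxes shown to all subjects. The coding, written on the first line of that list, is "0-no; 1-yes; default=no". The item has no not-applicable code and no skip rule tied to the maintenance drug.
- **Who is analysed.** Under section 10.3, "the analyses will be performed on the total sample monitored". The same section adds "Subgroup analyses are not anticipated", although the Steering Committee may ask for post-hoc ones.
- **How reasons are analysed.** Section 10.4.3: "These will be tabulated by choice and compared, if appropriate, by chi square test or by ordinal logistic regression". No section gives a separate denominator for any reason or stratifies reasons by maintenance drug.
- **What is recorded.** Section 8.3.2 d includes "type, dosage and duration of the maintenance anticoagulation performed", and the baseline form stores the drug by class.

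**The concern.** A subject maintained on a NOAC or LMWH has no INR target to miss. That subject is stored as no, exactly like a VKA subject whose INR was well controlled. The proportion citing the reason within each choice is then a product of two quantities: the share of VKA users in that choice, and how often VKA users in that choice cite INR trouble. A chi square or ordinal logistic regression on the total sample cannot separate the two.

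Unequal VKA shares across choices are plausible. Section 6.1 notes that the local healthcare system limits how long some regimens can continue, and section 10.2 expects country to matter. The documents do not, however, say that the shares differ.

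The reasons are a named secondary endpoint (8.1.2), and the synopsis places them within the primary objective. At stake is whether a difference between choices in this reason may be read as INR trouble steering the decision.

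**Working it through.** **The plan's own figure.** The documents give no power or error figure for the reasons. The nearest is the 90% power for the primary goodness-of-fit test (10.2): N = 3,200, alpha 0.05, 2 degrees of freedom, one option at 36.3%. Taking the other two as equal (31.85% each), w² = Σ(p − 1/3)²/(1/3), so w = 0.0629. Then λ = 3,200 × w² = 12.67 and power is 90.0%. The stated figure reproduces, and the same noncentral chi square method is used below.

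**Inputs.** N = 3,200 and three choices come from section 10.2. Alpha 0.05 is taken for illustration. VKA shares by choice, citation rates and group sizes are assumptions, so ranges are shown. Group sizes are equal thirds, or 1,920/480/800.

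**Formula.** For choice j:

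- proportion ticked: p_j = (VKA share)_j × (citation rate among VKA users)_j
- λ = Σ n_j (p_j − p̄)² / [p̄(1 − p̄)], referred to a noncentral chi square with 2 degrees of freedom.

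**One case in full.** Equal groups, VKA shares 30/40/50%, 20% of VKA users citing INR trouble in every choice. The ticked proportions are 6%, 8% and 10%, with mean 8%. λ = 1,066.7 × (0.02² + 0 + 0.02²)/(0.08 × 0.92) = 11.59, so the total-sample test rejects 87.2% of the time although VKA users cite the reason equally often.

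**All cases with equal citation among VKA users.** Rejection rate of the total-sample test in %, equal groups / 1,920-480-800:

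| VKA share by choice | cited by 5% | 10% | 20% | 30% |
|---|---|---|---|---|
| 40/40/40 | 5 / 5 | 5 / 5 | 5 / 5 | 5 / 5 |
| 38/40/42 | 5.8 / 5.9 | 6.7 / 6.9 | 8.7 / 9.1 | 10.9 / 11.6 |
| 35/40/45 | 10.5 / 11.3 | 16.8 / 18.6 | 31.2 / 35.0 | 46.4 / 51.7 |
| 30/40/40 | 13.2 / 14.6 | 22.7 / 25.8 | 43.2 / 49.1 | 62.4 / 69.1 |
| 30/40/50 | 29.5 / 34.5 | 54.9 / 62.9 | 87.2 / 92.4 | 97.6 / 99.0 |

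Restricted to VKA users, the test rejects 5% in every cell. Simulation (4,000 studies per scenario, equal groups, citation 5-20%) gave 4.4-5.7% for the restricted test and agreed with the formula for the total sample.

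**A real difference hidden.** Equal groups, VKA shares 50/40/30%, citation among VKA users 12/15/20%. The products are 0.50 × 0.12 = 0.40 × 0.15 = 0.30 × 0.20 = 6%, so λ = 0 and the total-sample test rejects 5%. Among VKA users (533, 427 and 320 subjects; pooled rate 15%), λ = (533.3 × 0.03² + 0 + 320 × 0.05²)/(0.15 × 0.85) = 10.04, which gives 82% power (81% by simulation).

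**Price of restricting when shares are equal.** With 40% VKA in each choice and citation of 5/10/15%, power is 99.2% on the total sample and 99.5% among VKA users.

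**The case against.** **No null is stated for the reasons.** A reader might call the percentages in the table false-positive rates of the planned test. The documents do not support that. If the question is whether the reason is cited equally often in each choice, the total-sample test answers it, and with unequal VKA shares the proportions really do differ. The table shows how often that test rejects when citation among VKA users is equal, which is a different question. It is nevertheless the one needed to interpret a difference as INR trouble influencing the choice.

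**The overall percentage is not biased.** With 40% on a VKA and 20% of them citing the reason, the table would show 8%. A reader might see this as understating a true 20%. It does not: 8% is the correct share of all decisions in which the reason was cited. This objection stands in full.

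**The VKA-only reading is an inference.** The documents nowhere say that the INR reason requires a VKA. The CRF can hold more than one drug class, and a physician might tick the box for an earlier or anticipated VKA. This stands, and means that such ticks must not be discarded.

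**Other reasons.** A reader might extend the point to pulmonary hypertension, because the index-episode form says "is NA with date blank if Type of event = 1 or 2". That is a skip rule in a sub-form for pulmonary embolism. It does not say that a DVT subject cannot have pulmonary hypertension; the help box is not limited to embolism, and heart failure and chronic respiratory disease are recorded for everyone. The point therefore does not extend to that item.

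**Status.** Section 10.3 says who is analysed, not the denominator of each item. The analyses are exploratory, the comparison is made only where judged appropriate, and post-hoc subgroups are allowed. All true, and it limits the weight of the point. But with default-no coding and no other rule, the working denominator is everyone, and a subgroup on request is not a plan.

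**Conclusion.** The point holds for the between-choice comparison of one reason. As planned, that comparison mixes the VKA share with citation among VKA users and can err in either direction. On assumed inputs the distortion is nil with equal shares, small at 38/40/42% (about 6-12% rejection for citation of 5-30%), moderate at 35/40/45% (about 10-52%) and severe at 30/40/50% with frequent citation (up to 99%). In the masking example, power falls from 82% to 5%.

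A reader might go further and infer that the test mainly detects which maintenance drug was used. The documents give no VKA share, overall or by choice, and no citation rate, so they do not support this. Nor does section 10.4.3 plan a comparison of reasons between countries.

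The primary endpoint analysis is unaffected.

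**What to change.** In section 10.4.3:

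1. Keep the total-sample tabulation of the INR reason by choice, as description.
2. Base the between-choice comparison of this reason on subjects whose recorded maintenance drug was a VKA, or stratify it by maintenance class.
3. Show that denominator beside the percentage, and list separately any ticks in subjects without a recorded VKA.

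Sections 8.1 and 8.1.1 describe extended anticoagulation as staying within the same class, whereas section 6.2 also allows another anticoagulant class. These sections must be reconciled, so that it is clear under which choice a subject moving from a VKA to another class is counted when this reason is read.

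**Cost.** A sentence or two in the plan and a filter on a field already collected; no new data and no change to care. The denominator shrinks and intervals widen for this item. For example, with equal groups and 40% on a VKA, the 95% half-width per choice is 1.96 × √(0.20 × 0.80/427) = 3.8 points around 20% among VKA users, against 1.96 × √(0.08 × 0.92/1,067) = 1.6 points around 8% in the total sample.

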## 6. Rationale and justification

### 6.1 Background

The reference international guidelines [1] recommend initial treatment of DVT of the lower limbs and/or PE with a direct anticoagulant (oral or parenteral) followed by a period of anticoagulation therapy with the same direct oral anticoagulant or partially overlapping it with a Vitamin K antagonist (VKA), with a preference for the former alternative.

An exception is represented by a VTE associated with an active cancer. In this case, a treatment with parenteral anticoagulant (in particular LMWH) for the whole period of 3 months is recommended.

Anticoagulation therapy is essential for at least three months in all cases. The incidence of VTE recurrence is considered to be very low when an event is triggered by surgery or another specific risk factor. In these cases, a three-month treatment is considered sufficient. In case of idiopathic (unprovoked) events, however, such period may not be sufficient due to the marked tendency of VTE to recur. In these cases, it is advisable to assess each subject's specific benefit (expected decrease in recurrences) in comparison with the risk of bleeding associated with prolonged anticoagulation, and determine the duration of anticoagulation based on this evaluation. However, pre-determined time-limited courses of therapy longer than 12 months are unusual [1]. In addition, based on the local healthcare system, not all regimens can be protracted indefinitely in all cases.

At the end of the three months – or longer, usually not more than one year – of anticoagulation, the attending physician has to decide whether and how to manage the long-term secondary prevention of recurrences, based on an assessment of the individual ratio of risks of recurrence and of bleeding. These individual estimates are often difficult to evaluate. A number of additional factors also influence the decision, including subject's predicaments and preferences, concurrent diseases and treatments, healthcare system support, and availability of potentially effective alternative treatments, such as aspirin [2] and sulodexide [3].

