#### 8.1.2 Secondary endpoints

The secondary endpoints include:

- the distribution of the reasons that were considered relevant by the attending physician to take the decision indicated as primary endpoint;
- the rate of thromboembolic complications and the combined rate of bleeding requiring at least an interview with the attending physician (major or clinically relevant non-major bleeding), or death from any cause during the 2-year follow-up.

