### 10.2 Sample size

The study anticipates recruiting approximately 3,200 subjects, based on considerations relevant to the primary endpoint.

The primary endpoint is the decision taken by the attending physician at the end of the maintenance anticoagulation initiated after the index event. Three options are possible: continue with extended anticoagulation (regardless of individual drug and dose), replace the anticoagulation with an antithrombotic, non-anticoagulant treatment, or stop any pharmacological prophylactic treatment.

In absence of other determinants, the null hypothesis is that the distribution of subjects by option is uniform. The analysis can therefore be performed with a goodness-of-fit test with 2 degrees of freedom. The alternative hypothesis is that at least one of the three choices is selected in a greater proportion than the other two. This analysis is performed once only at the end of recruitment.

With approximately 3,200 subjects, the study has 90% power to detect with 95% confidence a deviation from the uniform distribution, in case one of the options is selected in a proportion exceeding by 10% relative or more the proportion expected from the uniform distribution (i.e., in 36.3% or more of the subjects) [7].

Given that the factor “country” (synonymous of “healthcare system”) will be a likely cofactor in the analyses, the sample should be split across the participating countries in such a way to allow a reliable representativeness also for the smaller countries. The limit was considered not less than 100 subjects per country. The anticipated contribution by country was therefore estimated as:

Country	cases
China	approximately 200
Czechia	approximately 350
Mexico	approximately 300
Poland	approximately 900
Portugal	approximately 350
Romania	approximately 250
Russia	approximately 800
Slovakia	approximately 150
Tunisia	not less than 100

Since in this study the secondary endpoints are of clinical relevance as well, it is appropriate to estimate whether the indicated sample can yield reliable information also in relation to such endpoints.

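### The baseline tick-list of reasons has no item for healthcare-system or reimbursement limits and no general *other; specify*, although section 6.1 names the healthcare system as an influence on the decision

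*Combined protocol and SAP*

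**What the plan says.** Section 8.1.2 lists as the first secondary endpoint "the distribution of the reasons that were considered relevant by the attending physician to take the decision indicated as primary endpoint". The synopsis goes further and puts the reasons in its statement of the primary objective, beside the decisions themselves.

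Section 6.1 describes what bears on the decision. Besides the risks of recurrence and bleeding, it lists "healthcare system support, and availability of potentially effective alternative treatments". Earlier in the same section it notes that "based on the local healthcare system, not all regimens can be protracted indefinitely in all cases". Section 10.2 equates country with healthcare system, says that this factor "will be a likely cofactor in the analyses", and sets a minimum of 100 subjects per country for that purpose.

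The instrument is the table of reasons in the baseline part of the CRF template (Appendix IV), with the instruction "please tick all what applicable". Its only economic item is "Cost for the patient". Section 10.4.3 tabulates the reasons by choice.

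**The concern.** Section 6.2 gives two gaps in knowledge as the motive for the study: whether the split between options is the same across healthcare systems, and why physicians decide as they do. Where these meet, the question is whether physicians in some countries stop or switch because the system leaves them no other course. A closed list with no place for that answer cannot report it as a distinct reason.

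Section 7.2.2 says that there is so far no indication of which factors explain the decision. When the determinants are unknown, an open category is the usual safeguard against a list drawn too narrowly, and this list has none. At stake is how well the reasons table can be interpreted. The primary analysis of the choice is unaffected.

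**Working it through.** No arithmetic beyond a count applies. The check sets the influences named in section 6.1 against the items on the list.

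| Influence in section 6.1 | Item on the reasons list |
|---|---|
| Risk of recurrence | Own item, graded |
| Risk of bleeding | Own item, graded, plus a prior major bleed |
| Patient preference | Patient's choice |
| Concurrent disease | Cancer, renal insufficiency, worsening general condition |
| Healthcare system support | None; patient cost overlaps in part |
| System limit on how long a regimen can continue | None; patient cost overlaps in part |
| Availability of alternative treatments | None |

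**Count.** The list has 21 reasons, followed by two questions on whether the patient and the GP took part in the choice. Three of the 21 are non-clinical: the family doctor's decision, the patient's choice and cost for the patient. The other 21 − 3 = 18 are clinical or laboratory items. Items for a healthcare-system or reimbursement limit: 0 of 21. General open categories: 0 of 21. Partial proxies: 1 of 21 (patient cost). Free text is offered only under thrombophilia and contraindications.

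**What happens to a system-driven decision.** Suppose that a physician would have continued a drug but the local system will not renew it. The form allows three outcomes:

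1. The physician ticks patient cost, if the patient would have to pay. The system limit is then merged with personal affordability.
2. The physician ticks other reasons that also apply. The record is true but incomplete.
3. The physician ticks nothing. The first row of the table prints a default of *no*, and no check for at least one tick is shown, so a blank cannot be told from a considered *no*.

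In none of the three can the analyst separate the system limit from other reasons.

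**Whether another part of the plan fills the gap.** Section 10.4.2 allows country to be tested as a factor in the choice, if appropriate. That could show that countries differ in what they decide. It would not show that physicians gave a system limit as the reason, and it says nothing about variation within a country. Section 10.4.3 states no breakdown of reasons by country.

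**The case against.** The strongest reply is that the list is less closed than it looks. It has three non-clinical items and allows several ticks. When reimbursement ends, the patient may have to pay, and the cost item records that. A reader might infer that affected physicians are forced to give false clinical reasons or none at all. The form does not support that: their ticks may all be true, and the fault is omission or merging.

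Second, the healthcare-system question has its own route through country, and section 10.1 calls all analyses descriptive and exploratory, with physicians' attitudes left to later dedicated research. This limits the consequence, but the country route does not yield a stated reason.

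Third, the CRF is not uniform. The index-event, thrombophilia, treatment and complication lists have an open category. The list of current medications has no general one, and the concurrent-disease list has an *other* box with no field to specify it. So the reasons list is not the only one of its kind, and the case for an open category rests on the endpoint rather than on consistency.

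Fourth, availability of alternatives in section 6.1 may mean that options such as aspirin and sulodexide exist, not that a drug is missing from a local market. That reading is fair. The point therefore rests on system support and limits on duration, which are stated plainly.

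Fifth, sections 8.3.3 and 8.5 make the hospital record the data source and foresee queries against it. A reason noted there could be recovered, so the loss is not certain to be permanent. Recovery would depend on what each centre happened to write down.

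What stands is that a driver named in the plan has no category of its own and no open category to catch it.

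**Conclusion.** The point holds as a gap in measurement. Followed as written, the plan cannot identify healthcare-system or reimbursement limits as a distinct reason for the decision.

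Its size in subjects cannot be given. A reader might apply an assumed share of system-driven decisions to the planned 3,200 subjects and call the result misrecorded. The documents give no such share, do not say in which countries such decisions would cluster, and leave open how many would be caught under cost.

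A reader might also infer that the table would lead the study to conclude that system limits play no part. That goes too far: a table cannot show the absence of a reason that was never offered, and differences in choice between countries can be reported beside it. The narrower risk is that the table is read as a full account of why physicians decide as they do.

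The conclusion assumes that the reasons table is complete in the text available to this review. It runs without a break from first item to last, but nearby CRF content is missing, such as the decision options and the criteria help boxes. The absence should be confirmed on the original form.

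**What to change.** Add two items to the baseline list of reasons: a limit of reimbursement or prescription duration in the healthcare system, and *other; specify*. A third item, treatment not available locally, is optional, given the ambiguity in section 6.1. In section 10.4.3, state that reasons will be tabulated by country as well as by choice.

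A check that at least one reason is ticked before the page closes would be a useful optional addition, because it separates a blank from a *no*. It is not needed to close the gap.

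The cost is two or three tick-boxes on an existing e-CRF page and one more table, with no extra visit. Free text under *other* must be coded. If recruitment has begun, earlier subjects were not offered the new items, so the table must be shown by CRF version.
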